2.4.4 Analyses of safety data

In general, for PAP, the summary of safety results will be presented by study cohort and treatment arm. For the overall avalglucosidase alfa treatment period, the summary of safety results will be presented by initial planned dose levels among avalglucosidase alfa patients. For Cohort 3 alglucosidase alfa patients, the summary of safety results for ETP will be presented in separate tables.

In the PAP analysis, the safety analyses will be carried out with patients by the actual treatment received, irrespective of the treatment the patient has been randomized to. The actual treatment received is defined as:

- avalglucosidase alfa if the patient receives at least one infusion with this drug in PAP;
- alglucosidase alfa if the patient only receives alglucosidase alfa in PAP.

In the ETP analysis and/or overall evaluation of avalglucosidase alfa safety, the safety analyses will be carried out by the following 3 groups:

- AVAL/AVAL in ETP includes data in ETP among patients who received avalglucosidase alfa in PAP and ETP;
- ALGLU/AVAL in ETP includes data in ETP among patients who received alglucosidase alfa in PAP and received avalglucosidase alfa in ETP;
- AVAL/AVAL and ALGLU/AVAL in overall avalglucosidase alfa treatment period includes data in PAP and/or ETP among patients who received avalglucosidase alfa in that period.

General rules

All safety analyses will be performed on the safety population as defined in [Section 2.3.1](#), unless otherwise specified, using the following common rules:

- The safety baseline value is defined the same as the baseline definition in [Section 2.1.1](#).
- The potentially clinically significant abnormality (PCSA) values are defined as abnormal values considered medically important by the Sponsor according to predefined criteria/thresholds based on literature review and defined by the Sponsor for clinical laboratory tests, vital signs, and ECG (PCSA version dated January 2014 [[Appendix B](#)]).
 - PCSA criteria will determine which patients had at least 1 PCSA during the treatment epoch (for PAP and ETP respectively), taking into account all evaluations performed during this period, including nonscheduled or repeated evaluations.
 - The number of all such patients will be the numerator for the on-treatment PCSA percentage; the denominator will be the number of patients assessed for that given parameter in the treatment epoch by treatment group on the safety population.

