- For the overall evaluation of avalglucosidase alfa safety, selected analysis will be repeated by dose levels among avalglucosidase alfa patients
- The analysis of the safety variables will be essentially descriptive and no inferential testing is planned.

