Appendix B Potentially clinically significant abnormalities criteria

Measures	Adult Criteria	Pediatric Criteria
Liver function tests		
ALT	>3 x ULN	$\geq 3 \times \text{ULN}$
	>5 x ULN	$\geq 5 \times \text{ULN}$
	>10 x ULN	$\geq 10 \times \text{ULN}$
	>20 x ULN	$\geq 20 \times \text{ULN}$
AST	>3 x ULN	$\geq 3 \times \text{ULN}$
	>5 x ULN	$\geq 5 \times \text{ULN}$
	>10 x ULN	$\geq 10 \times \text{ULN}$
	>20 x ULN	$\geq 20 \times \text{ULN}$
Alkaline Phosphatase	>1.5 x ULN	$\geq 1.5 \times \text{ULN}$
Total Bilirubin	>1.5 x ULN	$\geq 1.3 \times \text{ULN}$
	>2 x ULN	
ALT and Total Bilirubin	ALT >3 x ULN and Total Bilirubin >2 x ULN	ALT $\geq 3 \times \text{ULN}$ and Total Bilirubin $\geq 2 \times \text{ULN}$
Hematology		

White Blood Cell (WBC)	<3.0 GIGA/L (non-Black), <2.0 GIGA/L (Black), ≥16.0 GIGA/L	Birth/0 to 27 days old (Neonates) <4.0 GIGA/L >25.0 GIGA/L 28 days/1 month to 23 months old (Infants) <4.0 GIGA/L >20.0 GIGA/L 24 months/2 years to <6 years old (Children) >3.0 GIGA/L >16.0 GIGA/L 6 to <12 years old (Children) <5.0 GIGA/L >17.0 GIGA/L 12 to 16/18 years old (Adolescents) <4.5 GIGA/L >13.5 GIGA/L
Lymphocytes	>4.0 GIGA/L	Birth/0 to 27 days old (Neonates) <1.2 GIGA/L >17.0 GIGA/L 28 days/1 month to 23 months old (Infants) <2.0 GIGA/L >13.5 GIGA/L 24 months/2 years to <6 years old (Children) <1.0 GIGA/L >9.5 GIGA/L 6 to <12 years old (Children) <1.0 GIGA/L >8.0 GIGA/L 12 to 16/18 years old (Adolescents) <0.6 GIGA/L >6.0 GIGA/L

Neutrophils	<1.5 GIGA/L (non-Black) <1.0 GIGA/L (Black)	Birth/0 to 27 days old (Neonates) <4.0 GIGA/L (1 day old) <1.5 GIGA/L (2 – 7 days old) <1.25 GIGA/L (>7 day – 1 month old) >1 ULN 28 days/1 month to 23 months old (Infants) <1.0 GIGA/L (1 – 3 months) <1.2 GIGA/L (3 – 24 months) >1 ULN 24 months/2 years to <6 years old (Children) <1.2 GIGA/L >1 ULN 6 to <12 years old (Children) <1.2 GIGA/L >1 ULN 12 to 16/18 years old (Adolescents) <1.2 GIGA/L >1 ULN
Monocytes	>0.7 GIGA/L	
Basophils	>0.1 GIGA/L	
Eosinophils	>0.5 GIGA/L or >ULN if ULN \geq 0.5 GIGA /L	>0.5 GIGA/L Or >ULN if ULN $>$ 0.5 GIGA/L

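### SAP Appendix B prints the lower white-cell PCSA limit for ages 2 to <6 years with a greater-than sign, so nearly every count is flagged and no low count is

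*SAP*

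**What the plan says.** SAP Appendix B lists PCSA limits by measure, with paediatric limits by age band. For white cells at 24 months to under 6 years it prints ">3.0 GIGA/L >16.0 GIGA/L".

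Neighbouring entries in the same appendix read differently:

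- White cells, 28 days to 23 months: "<4.0 GIGA/L >20.0 GIGA/L".
- White cells, 6 to <12 years: "<5.0 GIGA/L >17.0 GIGA/L".
- Lymphocytes, 2 to <6 years: "<1.0 GIGA/L >9.5 GIGA/L".
- White cells, adult column: lower limits of <3.0 (non-Black) and <2.0 (Black), and an upper limit of ≥16.0.

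SAP 2.4.4 makes the appendix the working definition: "PCSA criteria will determine which patients had at least 1 PCSA during the treatment epoch". Unscheduled and repeat values count, and for the percentage "the denominator will be the number of patients assessed for that given parameter". SAP 2.4.4.3 uses the appendix for laboratory PCSA incidence, primarily in the 25-week primary analysis period (PAP), and also calls for individual listings of PCSA patients.

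**The concern.** A two-sided laboratory rule needs a lower and an upper limit. Here both limits are upper limits, so the higher one does nothing and low counts have no limit at all. The rule as printed cannot be the one intended.

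Safety is the primary objective and haematology is part of the primary endpoint, so this table will be read. The band is also likely to be in use. Protocol I 03 admits patients under 18 years, and I 05 requires at least 6 months of prior alglucosidase alfa, which rules out the neonatal band. That leaves four usable paediatric bands, of which this is one.

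With the printed sign, the white-cell PCSA line would largely count how many children are aged 2 to <6 years. Groups could then differ on that line through age mix alone, and the difference could be read as an effect of treatment or dose.

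**Working it through.** **Step 1: is the entry out of pattern?** I counted the paediatric haematology entries in Appendix B that have both a lower and an upper side. Extra neutrophil lower limits for age sub-bands are counted within their band. The eosinophil entry is left out because it is a single upper limit with a condition on the normal range.

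| Measure | Entries | Less-than lower limit paired with greater-than upper limit |
|---|---|---|
| White cells | 5 | 4 |
| Lymphocytes | 5 | 5 |
| Neutrophils | 5 | 5 |
| Haematocrit | 3 | 3 |
| Platelets | 1 | 1 |
| Total | 19 | 18 |

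The one exception is white cells at 2 to <6 years.

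**Step 2: the printed rule against a lower-limit reading.** As printed, a count is a PCSA if it is >3.0 or >16.0. With the first sign reversed, it is a PCSA if it is <3.0 or >16.0.

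| White-cell count (GIGA/L) | As printed | First limit read as <3.0 |
|---|---|---|
| below 3.0 | not flagged | flagged |
| exactly 3.0 | not flagged | not flagged |
| above 3.0, up to 16.0 | flagged | not flagged |
| above 16.0 | flagged | flagged |

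The readings agree only at exactly 3.0 and above 16.0. As printed, the 16.0 limit never adds a flag, because every count above 16.0 is already above 3.0.

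**Step 3: comparison with adjacent bands.** Counts that are not PCSAs run from 4.0 to 20.0 in infants and from 5.0 to 17.0 at 6 to <12 years. Both ranges lie wholly above 3.0, so every such count would be flagged at 2 to <6 years. Test counts of 5, 8 and 12 are flagged in this band and in none of the other four paediatric bands. Test counts of 1, 2 and 2.9 are flagged in those four bands and not in this one.

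**Step 4: what else would catch low counts?** The neutrophil and lymphocyte entries for the same ages keep their lower limits, <1.2 and <1.0. A child who trips neither has a total of at least 1.2 + 1.0 = 2.2 GIGA/L. With a differential available, any total below 2.2 must therefore trip one of those rows. Only totals from 2.2 to <3.0 can escape every low-count PCSA row.

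**Step 5: size.** Haematology is scheduled twice on treatment in the PAP, at Weeks 13 and 25 (Protocol 10.1.2.6). One PCSA is enough to count a patient, so a child in this band is flagged unless all on-treatment counts are 3.0 or lower. With all planned patients assessed, each child not otherwise flagged adds:

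- 1/5 = 20 percentage points in a group of 5, the planned minimum per Stage 1 cohort or Cohort 3 arm;
- 1/10 = 10 points in a pooled group of 10;
- 1/20 = 5 points across about 20 patients.

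**The case against.** The strongest objection is provenance. The finding rests on one character in text read from a PDF by a program, and other cells in Appendix B also read oddly. A misread cannot be excluded. Against that, the other signs in the same cell read as expected. This objection stands as a reason to look at the source page first.

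The appendix also reproduces a sponsor standard: SAP 2.4.4 cites a version dated January 2014, and SAP 1.6 records a PCSA update. The programs may draw on that standard rather than on the printed table, and the documents do not show whether any program used the printed sign. That also stands. It is why the size is conditional, but the SAP entry would still be wrong as written.

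Finally, the harm is small. Safety analysis is descriptive, and "no inferential testing is planned". By-visit summaries, normal-range classification and worst-value comparisons do not use these limits. Counts above 16.0 are flagged under either reading, and most very low totals are caught by the differential rows. All of this is correct. None of it offsets the false flags between 3.0 and 16.0.

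**Conclusion.** The concern holds. As printed, the entry flags every white-cell count above 3.0 GIGA/L at ages 2 to <6 years, flags no low count, and makes its own second limit redundant. The internal evidence points to a reversed first sign.

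The effect is 20, 10 or 5 percentage points per affected child in groups of 5, 10 or 20. These figures assume that the printed limit is the one programmed, that everyone in the group is assessed, and that the child would not otherwise be flagged. The number of children in the band is not given, so the total effect cannot be stated.

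The damage is limited to the descriptive white-cell PCSA line and listing. No inference depends on it. Confidence is moderate until the sign has been seen on the source page.

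**What to change.** 1. Check the entry on the source page and against the sponsor's PCSA standard. If the page already shows a less-than sign, no change is needed.
2. Otherwise change the first limit to a lower limit. Use <3.0 GIGA/L only if the standard confirms the value: the adult column supports 3.0, but the adjacent paediatric bands use 4.0 and 5.0.
3. Check the programmed limit for this band, and rerun only white-cell PCSA tables and listings already produced with the printed limit.

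The cost is one table entry in the SAP and a check of one programmed limit.

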2.1.3.3 Laboratory safety variables

The clinical laboratory data consist of blood analysis (including hematology and biochemistry) and urinalysis. Clinical laboratory values after conversion into standard international units will be analyzed, and international units will be used in all listings and tables.

Blood samples for clinical laboratories will be taken as specified in the study protocol. The laboratory parameters will be classified as follows:

- Hematology: red blood cell count, hematocrit, hemoglobin, white blood cell count with differential count (neutrophils, eosinophils, basophils, monocytes, and lymphocytes), platelets.
- Biochemistry:
 - Plasma/serum electrolytes: sodium, potassium, chloride, calcium;

- Liver function: AST, ALT, alkaline phosphatase, gamma-glutamyl transferase, total and direct bilirubin;
- Renal function: creatinine, blood urea nitrogen, uric acid;
- Metabolic panel: glucose, albumin, total proteins, total cholesterol, triglycerides;
- Potential muscle toxicity: CK, CK with MB fraction, lactate dehydrogenase;
- Brain natriuretic peptide (BNP).
- Urinalysis will include urine color, appearance, specific gravity, proteins, glucose, erythrocytes, leukocytes, ketone bodies, and pH to be assessed:
 - Qualitatively: A dipstick is to be performed on a freshly voided specimen for qualitative detection using a reagent strip;
 - Quantitatively: A quantitative measurement for protein, erythrocytes, and leukocytes count will be required in the event that the urine sample test is positive for any of the above parameters by urine dipstick (e.g., to confirm any positive dipstick parameter by a quantitative measurement).

2.1.3.4 *Vital signs*

Vital signs include heart rate, systolic and diastolic blood pressure, respiratory rate, temperature, and oxygen saturation.

2.1.3.5 *Electrocardiogram variables*

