Hemoglobin	Males: \leq 115 g/L (\leq 7.14 mmol/L), \geq 185 g/L (\geq 11.48 mmol/L) Females: \leq 95 g/L (5.9 mmol/L), \geq 165 g/L (10.24 mmol/L) Decrease from Baseline \geq 20 g/L (1.24 mmol/L)	Birth/0 to 27 days old (Neonates) <86 mmol/L or 12.0 g/dL or any decrease $>$ 0.31 mmol/L or 2 g/dL 28 days/1 month to 23 months old (Infants) <1.40 mmol/L or 9.0 g/dL or any decrease $>$ 0.31 mmol/L or 2 g/dL 24 months/2 years to <16/18 years old (Children, Adolescents) <1.55 mmol/L or 10.0 g/dL or any decrease $>$ 0.31 mmol/L or 2 g/dL

Hematocrit	Males : ≤ 0.37 v/v, ≥ 0.55 v/v Females : ≤ 0.32 v/v, ≥ 0.5 v/v	Birth/0 to 27 days old (Neonates) <0.39 l/l or 40% >0.61 l/l or 47% 28 days/1 month to 23 months old (Infants) <0.29 l/l or 29% >0.42 l/l or 42% 24 months/2 years to <16/18 years old (Children, Adolescents) <0.32 l/l or 32% >0.47 l/l or 47%
RBC	≥ 6 TERA/L	
Platelets	<100 GIGA/L and 20% decrease from baseline ≥ 700 GIGA/L is missing	<100 GIGA/L >700 GIGA/L

ECG – PCSA criteria

HR	<50 bpm	Birth/0 to 27 days old (Neonates)
	<50 bpm and decrease from baseline ≥ 20 bpm	≤ 90 bpm and decrease from baseline ≥ 20 bpm
	<40 bpm	≥ 190 bpm and increase from baseline
	<40 bpm and decrease from baseline ≥ 20 bpm	≥ 20 bpm
	<30 bpm	28 days/1 month to 23 months old (Infants)
	<30 bpm and decrease from baseline ≥ 20 bpm	≤ 80 bpm and decrease from baseline
		≥ 20 bpm
		≥ 175 bpm and increase from baseline
		≥ 20 bpm
	>90 bpm	24 months/2 years to <6 years old (Children)
	>90 bpm and increase from baseline ≥ 20 bpm	≤ 75 bpm and decrease from baseline
	>100 bpm	≥ 20 bpm
	>100 bpm and increase from baseline ≥ 20 bpm	≥ 140 bpm and increase from baseline
	>120 bpm	≥ 20 bpm
	>120 bpm and increase from baseline ≥ 20 bpm	6 to <12 years old (Children)
		≤ 50 bpm and decrease from baseline
		≥ 20 bpm
		≥ 120 bpm and increase from baseline
		≥ 20 bpm
		12 to 16/18 years old (Adolescents)
		≤ 50 bpm and decrease from baseline
		≥ 20 bpm
		≥ 120 bpm and increase from baseline
		≥ 20 bpm
PR	>200 ms	Birth/0 to 27 days old (Neonates) ≥ 120 ms
	>200 ms and increase from baseline $\geq 25\%$	28 days/1 month to 23 months old (Infants) ≥ 140 ms
	> 220 ms	24 months/2 years to <6 years old (Children) ≥ 160 ms
	>220 ms and increase from baseline $\geq 25\%$	6 to <12 years old (Children) ≥ 170 ms
	> 240 ms	12 to 16/18 years old (Adolescents) ≥ 180 ms

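### The haemoglobin PCSA limits in SAP Appendix B use two unlabelled mmol/L scales, four-fold apart, for the adult and paediatric columns

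*SAP*

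**What the plan says.** SAP Appendix B gives each haemoglobin limit in two units.

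- **Adult column:** g/L comes first, with mmol/L in brackets. Examples are "95 g/L (5.9 mmol/L" for the female low limit and "20 g/L (1.24 mmol/L" for the fall from baseline.
- **Paediatric column:** mmol/L comes first and g/dL second. Infants have "<1.40 mmol/L or 9.0 g/dL or any decrease", patients from 2 years have "<1.55 mmol/L or 10.0 g/dL or any decrease", and the fall in every age band is "0.31 mmol/L or 2 g/dL". The neonatal cell reads "<86 mmol/L or 12.0 g/dL or any decrease".

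SAP 2.1.3.3 states: "Clinical laboratory values after conversion into standard international units will be analyzed". It does not say whether that means g/L or mmol/L for haemoglobin. The PCSA conventions in SAP 2.4.4 and 2.5.2 do not say which of two paired figures prevails.

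Under SAP 2.4.4 these limits decide which patients count as having a PCSA. SAP 2.4.4.3 then summarises PCSA incidence, mainly for the primary analysis period. Protocol 7.1 (I 03) admits only patients under 18, so the paediatric column governs at entry.

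**The concern.** The same 20 g/L fall is 1.24 mmol/L in one cell and 0.31 mmol/L in the neighbouring one. The two sets of mmol/L limits cannot both be right on one scale. A programmer who holds haemoglobin in mmol/L has no instruction on which scale the data must be on. The mmol/L figure is also the first one printed in every paediatric haemoglobin cell.

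What is at stake is the haemoglobin PCSA count. Laboratory evaluations, including haematology, belong to the protocol's primary (safety) endpoint. With approximately 20 patients planned, one patient wrongly flagged or missed moves a percentage by about 5 points (1/20) overall, and by more within a cohort.

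**Working it through.** All inputs are from the haemoglobin row of SAP Appendix B, except the creatinine figures in step 7, which are from its clinical chemistry section.

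**1. Adult factor (mmol per g).** 7.14/115 = 0.06209; 11.48/185 = 0.06205; 5.9/95 = 0.06211; 10.24/165 = 0.06206; 1.24/20 = 0.06200. The mean is 0.06206, and all five pairs agree.

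**2. Paediatric factor** (g/dL × 10 = g/L). Children and adolescents: 1.55/100 = 0.0155. Infants: 1.40/90 = 0.01556. Fall: 0.31/20 = 0.0155.

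**3. Ratio.** 0.06206/0.0155 = 4.00, and 0.06206/0.01556 = 3.99 for infants. Directly from the fall limits, 1.24/0.31 = 4.0.

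**4. Reproducing the stated paediatric figures.** The adult factor gives 6.21, 5.59 and 1.24 mmol/L for 100, 90 and 20 g/L, which is not what the table states. A quarter of it (0.01552) gives 1.55, 1.40 and 0.31, which is exactly what the table states. So the infant, child and fall entries are consistent among themselves, but on a different scale from the adult column.

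**5. What each choice of unit does.**

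| Limit | As stated in mass units | mmol/L figure read on adult scale |
|---|---|---|
| 2 years and older, low | 100 g/L | 1.55/0.06206 = 25.0 g/L |
| Infants, low | 90 g/L | 1.40/0.06206 = 22.6 g/L |
| Fall, all paediatric bands | 20 g/L | 0.31/0.06206 = 5.0 g/L |

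On the paediatric scale the adult limits fail instead. The male low limit becomes 7.14/0.0155 = 461 g/L, the female low limit 5.9/0.0155 = 381 g/L, and the fall 1.24/0.0155 = 80 g/L. In g/L throughout, the two columns sit together without conflict: lows of 90, 100, 95 and 115 g/L, and a fall of 20 g/L in both.

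**6. Neonatal cell.** 12.0 g/dL is 120 × 0.06206 = 7.45 mmol/L on the adult scale, or 120 × 0.0155 = 1.86 on the paediatric scale. The printed 86 is neither. It may be 1.86 with its leading characters lost, but the text available cannot show whether that happened in the SAP or when the PDF was read. No patient is affected: inclusion criterion I 05 requires at least 6 months of prior alglucosidase alfa.

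**7. Creatinine (separate and minor).** The table's other two paediatric pairs give 53/0.6 = 88.3 and 132/1.5 = 88.0 µmol/L per mg/dL. The 6 to <12 year pair gives 90/1.1 = 81.8. At about 88, 1.1 mg/dL is about 97 µmol/L, so the printed 90 and 1.1 differ by about 8%.

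**The case against.** The strongest reply is that nothing in the documents says haemoglobin is analysed in mmol/L. The adult column leads with g/L, every paediatric mmol/L figure has a g/dL figure beside it, and a program in g/L or g/dL would apply the table correctly. That stands. The harm needs two conditions together: data in mmol/L, and data on the adult column's scale. What the reply does not remove is the contradiction inside the row, or the absence of any rule that picks the unit.

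Four stronger readings are tempting, and the documents do not support them.

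- **Anaemia would go unflagged.** Only the absolute limit would stop firing. The criterion also includes a fall from baseline, which would trigger more readily on the adult scale. SAP 2.4.4.3 separately classifies laboratory values against the laboratory's normal ranges, lists haemoglobin for by-visit abnormality counts, and compares worst abnormalities with baseline. None of this uses the Appendix B limits.
- **A 5 g/L fall is trivial or within ordinary variation.** The documents give no within-patient variability. They show only that 5 g/L is a quarter of the stated 20 g/L.
- **Patients who reach 18 would change scale during the study.** The SAP does not say whether the column follows age at entry or age at assessment.
- **The primary safety conclusion is compromised.** SAP 2.4.4 makes the safety analysis essentially descriptive, without inferential testing. No haemoglobin limit appears among the laboratory triggers in Protocol 10.3.1 or the laboratory AESIs in 10.4.1.3.

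**Conclusion.** The row contradicts itself. Its mmol/L limits are on two scales, 4.0-fold apart, with no label, and the table's own figures are enough to show this. As written, no single mmol/L dataset can satisfy both columns.

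The consequence is conditional. If haemoglobin is programmed in mmol/L on the adult scale, the paediatric low limits shrink to about a quarter of what is stated and would in practice not fire, while the fall limit becomes four times as sensitive. If it is programmed in mmol/L on the paediatric scale, any patient assessed against the adult column is misclassified instead. If it is programmed in g/L or g/dL, there is no error. The mismatch itself is certain. Which unit the program uses cannot be learned from the documents. The effect is confined to haemoglobin PCSA counts and listings, so this should be corrected but does not threaten the trial's main conclusions.

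**What to change.** Name one unit for haemoglobin in the PCSA analysis, preferably g/L, in Appendix B or SAP 2.1.3.3. Use the table's own g/dL figures: infants <90 g/L, children and adolescents <100 g/L, fall >20 g/L. No new threshold is needed.

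Then either delete the paediatric mmol/L figures or re-express them on the adult column's scale: 90 × 0.06206 = 5.59, 100 × 0.06206 = 6.21 and 20 × 0.06206 = 1.24 mmol/L. Check the PCSA program against the corrected cells and confirm the unit in which the central laboratory delivers haemoglobin.

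In the same edit, tidy the neonatal mmol/L entry so that it agrees with its paired 12.0 g/dL, and reconcile the two creatinine figures for ages 6 to <12 years.

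The cost is a few cells in one appendix table and one program check. No data collection, design or sample-size element changes.
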